- That I will be responsible for maintaining each patient's consent form in the study file and provide each patient with a signed copy of the consent form.

Investigator Name and Title:

Institution Address:

Signature: _____

Date: _____

PROTOCOL SUMMARY

Title: *"Nitroglycerin vs. Furosemide using Lung Ultrasound Pilot Trial" (N-FURIOUS)*

[figure not shown]
Précis: Of the one million admissions for AHF in the US, approximately 80% are initially managed in the ED. Outcomes from AHF are poor: nearly 25% are dead or re-hospitalized within 30 days of discharge. The evidence base to treat AHF is limited. In fact, there are no pharmacologic therapies with Class I, Level A guideline recommendations. The acute

treatment of patients today is largely the same as 40 years ago. This proposal aims to build the evidence base for ED AHF care.

Using a two-site, randomized controlled design, this pilot study will test whether a nitrate intense strategy more effectively reduces congestion, defined by LUS B-lines, better than a diuretic intense strategy.

Objectives:	1: To determine whether a nitrate intense strategy safely reduces congestion, defined by LUS B-lines, better than a diuretic intense strategy. 2: To demonstrate feasibility of recruitment and compliance with study protocol to inform future study design and enrollment projections, an external site will also test our study protocol.
Endpoint	A comparison of total B-lines at the conclusion of ED AHF management or maximum of 6 hours after enrollment, whichever comes first.
Population:	Emergency department (ED) AHF patients. All patients who meet inclusion and no exclusion criteria will be enrolled during their ED visit within 3 hours of presentation.
Phase:	2
Number of Sites enrolling participants:	Two sites (3 total hospitals). Projected sample size, n=70.
Description of Study Agent:	Nitrate intense vs. Diuretic intense AHF treatment strategy
Study Duration:	2 years. There will be three months of start up, and one month of study conclusion work. Enrollment will occur over 20 months, which equals 3.5 patients month. As there will be staggered start up to determine replication, approximately 1-2 patients/month.
Participant Duration:	30 days post discharge

SCHEMATIC OF STUDY DESIGN

*whichever comes first

**Presentation is defined as first time recorded when placed in a room to be treated. This allows patients to still be enrolled despite a long waiting room time

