3 OBJECTIVES AND PURPOSE

Objectives:

1: To determine whether a nitrate intense strategy safely reduces congestion, defined by LUS B-lines, better than a diuretic intense strategy.

2. To demonstrate feasibility of recruitment and compliance with study protocol to inform future study design and enrollment projections, an external site will also test our study protocol.

Purpose:

This pilot trial is designed to provide the necessary and sufficient information for a larger, definitive trial.

Hypothesis 1a: Nitrate intense treated patients will have less congestion, defined by LUS B-lines, than diuretic intense patients at 6 hours after start of treatment.

Hypothesis 1b: Nitrate intense treated patients will have greater dyspnea relief than diuretic intense patients at 6 hours after start of treatment.

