4.2.1 PRIMARY ENDPOINT

The total number of B-lines at the conclusion of ED AHF management

Main Secondary Endpoints:

Dyspnea will also be assessed using a 5-point and 7-point Likert scale.

B-lines ≤ 15 at the conclusion of ED AHF management

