10.2 STATISTICAL HYPOTHESES

- *Hypothesis 1a: Nitrate intense treated patients will have less congestion, defined by LUS B-lines, than diuretic intense patients at 6 hours after start of treatment.*
- *Hypothesis 1b: Nitrate intense treated patients will have greater dyspnea relief than diuretic intense patients at 6 hours after start of treatment.*
- *Hypothesis 2: Each site (n=3) will enroll ~2 patient per month for 12 months.*

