10.4 DESCRIPTION OF STATISTICAL METHODS

10.4.1 GENERAL APPROACH

As a small, exploratory, pilot study, we are uncertain the difference, if any, between the two arms in regards to B-lines after treatment. Unless stated otherwise, two-sided p values < 0.05 will be considered statistically significant, without regard to multiple comparisons. Statistical tables and listings and analyses will be produced using SAS® release 9.1 or later (SAS Institute, Inc, Cary, NC, USA) or other validated statistical software.

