10.4.3 ANALYSIS OF THE PRIMARY EFFICACY ENDPOINT(S)

The total number of B-lines at the conclusion of ED AHF management

We will examine the distribution of B-lines measurements for the groups with and without events separately. Both absolute number and relative change will be evaluated. Receiver Operating Characteristic (ROC) curves will be plotted together with area under the curve (AUC) calculated to understand the prediction performance of the B-line measurements. Sensitivity, specificity, positive and negative predictive values will be computed at a number of thresholds of B-line measurements to understand the trade-off between false positive and false negative. Confidence intervals of statistical measures will be constructed using the bootstrap method.⁹¹ Although 15 B-lines have been previously identified as a valid threshold, an alternative number may be more useful in the ED setting.

Potential covariates will also be considered in a logistic regression setting to improve precision, which includes baseline co-morbidities, baseline medications (in particular guideline recommended therapies) in-hospital medications, baseline renal function, serum sodium, natriuretic peptide levels, troponin levels, renal function, baseline blood pressure, and discharge medications. Variables such as physical exam, other vital signs, and hemoconcentration may also be included. These covariates are known markers of risk and are standard of care assessments for the vast majority of AHF admissions. Covariates with univariately significant association with the outcome will be included together with the treatment indicator in a logistic regression model. Due to limited sample size, we will limit the number of covariates (including treatment indicator) such that there is 10 events per covariate.

ANALYSIS OF THE SECONDARY ENDPOINTS

1. Dyspnea will also be assessed using a 5-point and 7-point Likert scale.

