10.5 SAMPLE SIZE OVERALL

This pilot study is powered to show a difference of at least 7 B-lines between treatment arms. With a total of 70 subjects (i.e. 35 in each arm), we will have 82% power to detect an effect size of 0.7 on the number of B-lines, where the type I error rate is controlled at 0.05 (two sided)..

Local Sample Size: As a multicenter study, the expected enrollment at IU is half the patients or 35. However, up to 50 patients may be enrolled depending on accrual rates at the other site.

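### Section 10.4.3 gives no between-arm test of the B-line count and names two B-line measures without saying which, if either, decides Hypothesis 1a

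*Combined protocol and SAP*

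**What the plan says.** Section 4.2.1 names a single primary endpoint: "The total number of B-lines at the conclusion of ED AHF management". The protocol summary frames it as a comparison: "A comparison of total B-lines at the conclusion of ED AHF management or maximum of 6 hours after enrollment, whichever comes first". The first line under 10.4.3 repeats the 4.2.1 definition. Section 10.5 plans for a difference of at least 7 B-lines between arms and claims "82% power to detect an effect size of 0.7 on the number of B-lines", with 35 patients per arm and two-sided alpha 0.05.

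The body of 10.4.3 then turns to something else. It opens with "We will examine the distribution of B-lines measurements for the groups with and without events separately" and continues with "Both absolute number and relative change will be evaluated". ROC curves, AUC, sensitivity, specificity and predictive values follow. The next paragraph describes a logistic regression in which treatment is one indicator among covariates; the outcome of that model is not named.

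Hypothesis 1a in 10.2 reads "Nitrate intense treated patients will have less congestion, defined by LUS B-lines, than diuretic intense patients at 6 hours after start of treatment", and Objective 1 in section 3 is "To determine whether a nitrate intense strategy safely reduces congestion, defined by LUS B-lines, better than a diuretic intense strategy". Neither says whether congestion is measured by the final count or by a change. Section 10.4.1 adds that "two-sided p values < 0.05 will be considered statistically significant, without regard to multiple comparisons".

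**The concern.** A reader who follows 10.4.3 to the letter cannot produce the result that 10.5 was sized to deliver. Nothing there says to compare the count between the two arms, by what test or model, or with what adjustment. The only sentence in the section that names forms of the B-line variable names two and ranks neither.

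The two forms are different variables. A patient going from 100 to 50 lines and one going from 20 to 10 have the same relative change and very different final counts. Hypothesis 1a could be read on either.

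At stake is the meaning of the main result. The trial is unblinded (10.6.1), so the deciding analysis should be fixed before the data are seen. The type I error rate that 10.5 calls controlled belongs to one test on one variable. Section 3 says the pilot is to inform a larger, definitive trial, so the choice of variable and model would carry forward into that trial's sample size.

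**Working it through.** **1. The plan's own figure.** Inputs from 10.5: 35 per arm, difference 7 lines, effect size 0.7, two-sided alpha 0.05. The SD is not stated; it is implied as 7/0.7 = 10. For a two-sample t test:

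- noncentrality = 0.7 × √(35/2) = 2.928
- df = 68, critical value 1.995
- power = 82.3% (normal approximation 83.4%)

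The stated 82% reproduces. The sample size therefore presupposes one between-arm comparison of the count, and 10.4.3 does not contain it.

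**2. What 10.4.3 supplies, set against what 10.5 needs.**

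| Needed for Hypothesis 1a | In 10.4.3 |
|---|---|
| Outcome variable | Count in the first line; then absolute number and relative change, unranked |
| Groups compared | Patients with and without events |
| Test or model | ROC/AUC and accuracy measures; logistic regression, outcome unnamed |
| Role of treatment arm | An indicator in that logistic regression only |

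Relative change is in no primary or secondary endpoint list. Change in B-lines appears in 4.2.2 and 10.4.4 only, as an exploratory association with 30-day outcomes.

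**3. What the gap could cost if both measures were tested.** Suppose count and relative change were each tested between arms at two-sided 0.05 and either could carry the claim. The chance of at least one false positive is 1 − P(|Z₁| < 1.96 and |Z₂| < 1.96), which depends on the correlation between the two statistics:

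| Assumed correlation | False-positive rate |
|---|---|
| 0 (independent): 1 − 0.95² | 9.75% |
| 0.5 | 9.1% |
| 0.7 | 8.3% |
| 0.9 | 7.0% |

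A simulation of the two t tests used 35 per arm, final-count SD 10, baseline mean 40 to 60 with SD 10 to 20, baseline-final correlation 0 to 0.85, and 20,000 runs per scenario. It gave 7.9% to 9.6%. With a true 7-line difference the two tests disagreed on significance in 13% to 54% of runs. The documents give no baseline mean, SD or correlation, so all of these inputs are assumptions.

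**4. Power under the proposed analysis.** Adjusting for the T00 count reduces the residual SD to 10 × √(1 − r²), where r is the baseline-final correlation. The standardised effect becomes 0.7/√(1 − r²), with df = 67:

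| Assumed r | Residual SD | Effect size | Power, 35 per arm |
|---|---|---|---|
| 0 | 10.0 | 0.700 | 82.3% |
| 0.2 | 9.80 | 0.714 | 83.8% |
| 0.4 | 9.17 | 0.764 | 88.3% |
| 0.6 | 8.00 | 0.875 | 95.0% |

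**5. The alternative of letting both measures decide.** With Bonferroni at 0.025 each, power for the count falls to 73.7% at 35 per arm. Restoring 82% needs 42 per arm, 84 in total.

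**The case against.** A reader might infer that the plan gives Hypothesis 1a two chances at p < 0.05. The documents do not support that. The sentence on absolute number and relative change sits between one about patients with and without events and a run of ROC measures. In place, it most naturally describes two ways of expressing B-lines as a predictor of events. No between-arm test of relative change is written anywhere. The count is named as the endpoint in the summary, in 4.2.1 and at the head of 10.4.3, so a default deciding variable can be inferred. This part of the objection stands.

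A reader might also infer that the trial would report opposite conclusions on one hypothesis. The disagreement rates do not show this. They move widely with the assumed baselines, and much of the disagreement is one test detecting a real effect that the other misses. With baseline mean 60, SD 20 and no baseline-final correlation, for example, power was 82% for the count and 31% for relative change.

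Finally, 10.4.1 calls the study small and exploratory and openly waives multiplicity adjustment. That tempers the seriousness.

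None of this supplies the missing analysis. If the paragraph is about prediction, 10.4.3 has no between-arm comparison of the primary endpoint at all. Waiving multiplicity adjustment does not say which analysis is primary, and 10.5 still claims power and a controlled error rate for a comparison that is not described.

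**Conclusion.** The point holds as a gap in specification. The primary endpoint is defined and powered as a count, but its analysis section states no between-arm test of that count, leaves the outcome of its regression unnamed, and does not say whether absolute number or relative change decides Hypothesis 1a.

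The sample size is not in error: 82% power reproduces for one test with the implied SD of 10. The inflation to about 7% to 9%, with some assumed baselines reaching 9.6%, is conditional. It applies only if both measures were tested between arms and either could win, which the plan does not write. The gain from baseline adjustment is also conditional, on a correlation that the documents do not give; with no correlation there is essentially neither gain nor loss.

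**What to change.** In 10.4.3, state that Hypothesis 1a is decided by the between-arm comparison of the total B-line count at the primary time point, using a linear model (ANCOVA) with treatment arm and the T00 count, tested at two-sided 0.05. Label relative change as supportive, with no role in deciding the hypothesis. Move the text on events, ROC curves and predictive accuracy to 10.4.4, where the association of B-lines with 30-day outcomes already sits, and name the outcome of the logistic regression.

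This takes a few sentences and no new data, since the T00 scan is already in the schedule of events (7.3.4). N stays 70. Power for a 7-line difference with SD 10 is at least about 82%, rising to about 84%, 88% or 95% if the baseline-final correlation is 0.2, 0.4 or 0.6. The downside is that relative change cannot carry the primary claim.

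### With few events, ordinary bootstrap intervals for sensitivity, specificity, PPV and NPV under-cover near 0% or 100% and can have zero width (minor; exploratory analysis)

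*Combined protocol and SAP*

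**What the plan says.** Section 10.4.3 stands under the primary efficacy endpoint but describes a prognostic analysis. B-line counts are compared between patients with and without events, and ROC curves with AUC are drawn. "Sensitivity, specificity, positive and negative predictive values will be computed at a number of thresholds of B-line measurements", and the stated aim is to see how false positives trade against false negatives. One interval method is given for all of this: "Confidence intervals of statistical measures will be constructed using the bootstrap method". The type of bootstrap and the resampling unit are not stated.

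The section accepts 15 B-lines as an established threshold and adds that "an alternative number may be more useful in the ED setting". It gives no rule for choosing another number and no correction or validation if one is chosen. It does not say what an event is.

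The Protocol Summary gives a background figure for acute heart failure: "nearly 25% are dead or re-hospitalized within 30 days of discharge". Section 10.5 sets the sample size at 70. Sections 4.2.2 and 10.4.4 list the association of B-lines with 30-day outcomes as exploratory.

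**The concern.** Resampling can only reproduce what was observed. If every event lies above a threshold, every resample of the observed patients also shows 100% sensitivity, and the interval has no width. The same happens to specificity at high thresholds, and to PPV or NPV when all or none of the patients concerned are correctly classified. A scan over thresholds moves towards these ends. Just short of them the interval exists but is too short.

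A second issue arises only if the scan is used to pick a new cut-off. Accuracy reported from the patients who supplied the cut-off is too favourable, and an interval computed at that cut-off does not allow for the choice.

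Section 3 presents the pilot as the source of information for a larger trial. An overstated precision or accuracy figure could be carried forward as a design input.

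**Working it through.** **The plan's own figure.** Section 10.5 states "With a total of 70 subjects (i.e. 35 in each arm), we will have 82% power to detect an effect size of 0.7". The noncentrality is 0.7 × √(35/2) = 2.93. With 68 degrees of freedom and two-sided 5% this gives 82.3% power (83.4% by the normal approximation), so the 82% reproduces. It concerns the between-arm comparison. The documents give no precision figure for the ROC analysis.

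**Inputs.** N = 70 (Section 10.5). Event rate about 25% (Protocol Summary), so 0.25 × 70 = 17.5. I take 17 events and 53 non-events, with complete 30-day follow-up. This is an assumption, and 10 to 21 events (14% to 30% of 70) is shown as a range.

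**All events detected.** The bootstrap interval is 100% to 100%. The Clopper-Pearson lower limit for n out of n is 0.025^(1/n), and the Wilson lower limit is n/(n + 1.96²).

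- 17/17: exact 0.025^(1/17) = 80.5%; Wilson 17/20.84 = 81.6%.
- 10/10: exact 69%. 21/21: exact 84%.
- 53/53 (specificity): exact 93.3%.

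The chance of seeing 17/17 is 0.90^17 = 17% at a true sensitivity of 0.90, and 0.95^17 = 42% at 0.95.

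**Coverage of nominal 95% intervals at a fixed threshold.** Coverage is summed over the binomial distribution with the event count held at n. At n = 17 and true sensitivity 0.95, the percentile interval contains 0.95 only when 14, 15 or 16 events are detected: 0.041 + 0.158 + 0.374 = 0.573. The case 17/17 always misses. In full (%):

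| True value | Bootstrap, n=17 | Wilson, n=17 | Exact, n=17 | Bootstrap, n=53 | Wilson, n=53 |
|---|---|---|---|---|---|
| 0.50 | 95.1 | 95.1 | 95.1 | 94.7 | 94.7 |
| 0.70 | 91.0 | 94.0 | 96.8 | 95.0 | 95.0 |
| 0.80 | 87.1 | 94.0 | 96.7 | 94.2 | 96.2 |
| 0.85 | 92.9 | 96.8 | 99.2 | 94.5 | 96.8 |
| 0.90 | 81.1 | 97.8 | 97.8 | 89.6 | 93.9 |
| 0.95 | 57.3 | 95.0 | 99.1 | 91.8 | 95.2 |
| 0.98 | 29.0 | 95.5 | 99.6 | 65.7 | 97.8 |

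The columns are not smooth because the counts are discrete (0.85 at n = 17, for example). The pattern is still clear: sensitivity, on about 17 patients, suffers first; specificity, on about 53, fails only nearer the extreme.

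**AUC.** In simulation (17 events, 53 non-events, normal marker, 400 replicates of 300 resamples) percentile intervals for the AUC covered 93.5% at AUC 0.6 and 92.2% at AUC 0.7, close to nominal.

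**If a cut-off were chosen from the data.** The plan has no selection rule, so I assume the cut-off that maximises the Youden index (sensitivity + specificity − 1). Over 3,000 replicates, the apparent index against the true index of the chosen cut-off averaged:

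- AUC 0.5: 0.16 against 0
- AUC 0.6: 0.27 against 0.12
- AUC 0.7: 0.40 against 0.26
- AUC 0.8: 0.54 against 0.42

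At AUC 0.6 apparent sensitivity was 0.666 against a true 0.544, about 12 points too high; specificity was 0.606 against 0.576. Percentile intervals computed at the chosen cut-off, ignoring the choice, covered the true index or sensitivity 76% to 79% of the time (AUC 0.6 and 0.7).

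**The case against.** The strongest reply is that this is a descriptive table in a small exploratory pilot, and that the worst figures sit at thresholds nobody would adopt. With a normal marker, 95% sensitivity goes with specificity of only about 10% at AUC 0.6 and 18% at AUC 0.7. For the baseline count, entry already requires more than 15 B-lines (Section 5.1), so 100% sensitivity at a cut of 15 is a fact of design and not false certainty. This stands, and it limits the importance of the point. It does not remove it: coverage is already 87% at a sensitivity of 0.80, and a printed interval of 100% to 100% misleads in an exploratory table too.

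Several stronger readings are tempting, and the documents do not support them.

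- A reader might infer that all the prognostic error bars are wrong. They are not: the AUC and mid-range proportions are close to nominal.
- A reader might infer that every kind of bootstrap collapses. Section 10.4.3 names no type. In a trial calculation for 17/17 with a normal marker, a smoothed bootstrap gave an average lower limit of about 80% and a parametric one about 88%. The collapse belongs to ordinary resampling of the observed patients.
- A reader might infer that the plan picks a new cut-off and reports its accuracy uncorrected. It says only that another number might serve better, and describes the scan as showing a trade-off. The optimism figures are therefore conditional on a choice, and on the Youden rule supplied here.
- A reader might infer that delivering a cut-off to the next trial is an objective. Section 3 names the strategy comparison and feasibility; its purpose statement is general.

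**Conclusion.** The concern holds in a limited form. Applied as written with ordinary resampling, the stated method gives intervals for sensitivity, specificity, PPV and NPV that are too short near 0 or 1, and of zero width when all or none are correctly classified. With 17 events, 17/17 is reported as 100% to 100% where the exact interval is 80.5% to 100%. With 10 to 21 events the exact lower limit runs from 69% to 84%.

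The event count is an inference from a background rate. It would change if events included ED re-visits, which are also collected, or if follow-up were incomplete. The coverage figures assume a percentile bootstrap at a fixed threshold; PPV and NPV were not computed, because their denominators depend on the threshold. The optimism figures further assume a normal marker and a Youden choice.

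The between-arm comparison, the test of the binary endpoint at 15 B-lines and the sample size are untouched. Priority: minor.

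**What to change.** In Section 10.4.3:

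1. Define the event and the B-line measurement (baseline, end of ED management, discharge or change) used in the ROC analysis.
2. Use Wilson intervals for sensitivity, specificity, PPV and NPV, or Clopper-Pearson if a conservative interval is preferred.
3. Keep the bootstrap for the AUC, and state its type and that patients are the resampling unit.
4. If a cut-off other than 15 is proposed from these data, state the selection rule and label the cut-off hypothesis-generating. Repeat the search inside each bootstrap sample, apply each selected cut-off back to the full data, and subtract the average loss from the apparent sensitivity and specificity.

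Nothing is needed to protect 15 as the cut-off for the trial's own endpoint; Sections 4.2.1 and 10.4.3 already fix it.

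The cost is a few lines of SAP text and code, with no extra patients or data. Intervals become slightly wider, and the accuracy quoted for any new cut-off becomes less favourable.

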7.3.4 SCHEDULE OF EVENTS TABLE

Schedule of Events	Screening	Day 1 T00	Day 1 T02-04	Day 1 T06	Day 2-6 T24-D6	30 day follow up
Informed consent (I/E)	X					
Medical History	X					
Medication history	X					
Clinical Assessment#		X	X	X	X	
Body Weight, height, Vital Signs	ED SOC	VS only	VS only	VS only	BW/VS only	
5-point and 7-point Likert scale		X		X	X	
Labs: Electrolytes, hematology, NP, eGFR, Troponin	ED SOC					
12-lead ECG	ED SOC					
CXR	ED SOC					
LUS B-lines 8 zone	X (LUS T00)		X	X	X ^{^^}	
Nitrate vs. Diuretic intense management		X	X	X		
Lab draw: eGFR, Hgb/Hct [^]		X				
eCRF/data collection/verification		X				X
Assessment of AE/SAE's						X
Phone follow-up Vital Status						X

Subject payment		X				X
-----------------	--	---	--	--	--	---

SOC = standard of care, ED = Emergency Department, I/E = inclusion, exclusion, CV = cardiovascular, LUS = lung ultrasound, BW = body weight, NP = natriuretic peptide ^if collected as part of standard of care, will use that result. The last collected result will be used if not drawn on or close to discharge ^^ LUS to be performed up to 48 hours after hospitalization. If an obs unit patient, prior to discharge.

Further detail regarding timing of assessments: [NOTE: given clinical circumstances (i.e. left the ER for a test, discussion with consultant, etc) – the SITE PI has final discretion to continue to image a patient before or after the allotted window. This time MUST be recorded in the eCRF]

- T00: initial LUS scan (in ED for screening and eligibility)
- T02: 2-4 hours after initial treatment (in ED) (+/- 30 minutes)
- T06: 2-4 hours after T02 or pre-ED discharge, whichever comes first (+/- 60 minutes)
- T48: up to 48 hours after initial scan (Day 3) (+/- 12 hours)

** For vital signs during hospitalization. The nearest vital signs to the LUS exam will be captured.

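### No model is named for the between-arm comparison of the final B-line count, and the T00 count, available for every eligible randomized patient, is not prespecified as a covariate

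*Combined protocol and SAP*

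**What the plan says.** Section 4.2.1 of the combined protocol and SAP defines the primary endpoint as "The total number of B-lines at the conclusion of ED AHF management", a count after treatment. The schedule in 7.3.4 lists the baseline scan as "T00: initial LUS scan (in ED for screening and eligibility", and inclusion criterion 3 requires more than 15 lines on it. Every eligible randomized patient therefore has a T00 count.

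Section 10.4.3, on the primary analysis, describes B-line distributions in patients with and without events, ROC curves and thresholds. It then describes a logistic regression whose candidate covariates include "baseline co-morbidities, baseline medications (in particular guideline recommended therapies) in-hospital medications, baseline renal function, serum sodium, natriuretic peptide levels, troponin levels", with further optional variables. Covariates are chosen by univariate significance and limited to one per 10 events. T00 B-lines are not named. Baseline is used only implicitly: "Both absolute number and relative change will be evaluated", with no test or model attached.

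Section 10.5 states that "This pilot study is powered to show a difference of at least 7 B-lines between treatment arms" and that "With a total of 70 subjects (i.e. 35 in each arm), we will have 82% power to detect an effect size of 0.7", "where the type I error rate is controlled at 0.05 (two sided").

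Section 10.6.1 gives each site a blocked randomization table and states no stratification on B-lines.

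**The concern.** The plan names tests for baseline variables (10.4.2), the binary outcome of 15 or fewer lines (10.4.3), days alive and out of hospital (10.4.4) and safety variables (10.4.5). It names none for the arm difference in the continuous primary count. The reader has to infer an unadjusted comparison from 10.5.

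T00 is the same measurement as the endpoint, taken earlier, so it is a natural covariate. Entry has a floor but no ceiling, so starting counts may differ widely. With 35 per arm, part of any chance difference in T00 carries through to an unadjusted arm difference. At stake are the width of the interval and how far the estimate depends on the luck of the allocation. Section 3 says the pilot is meant to inform a definitive trial, so both matter later. The plan already accepts the principle: 10.4.3 wants covariates for precision, and 10.4.4 notes that adjustment can raise power for an exploratory endpoint.

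**Working it through.** **Inputs from the documents.** 35 per arm, difference 7 lines, effect size 0.7, two-sided alpha 0.05 (10.5). The SD is not stated; 7 / 0.7 = 10.

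**Assumed, because the documents do not give them.** The correlation rho between T00 and the final count, shown from 0.1 to 0.7, and a T00 SD of 10, the same as the implied outcome SD.

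**Step 1. Reproduce the plan's figure.** Two-sample t-test: noncentrality = 0.7 × √(35/2) = 2.93 on 68 df. Power is **82.3%**, which matches the stated 82%. The normal approximation gives 83.4%, and a one-sided normal calculation gives 90.0%, which does not match. The stated figure is therefore that of an unadjusted comparison.

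**Step 2. Adjust for T00.** Residual SD = 10 × √(1 − rho²). Effective effect size = 0.7 / √(1 − rho²), on 67 df.

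| rho | Residual SD | Power | Gain over 82.3% (points) |
|---|---|---|---|
| 0.1 | 9.95 | 82.7% | 0.4 |
| 0.2 | 9.80 | 83.8% | 1.5 |
| 0.3 | 9.54 | 85.7% | 3.4 |
| 0.4 | 9.17 | 88.3% | 6.0 |
| 0.5 | 8.66 | 91.5% | 9.2 |
| 0.6 | 8.00 | 95.0% | 12.7 |
| 0.7 | 7.14 | 98.1% | 15.8 |

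At rho = 0 the adjusted power is 82.28% against 82.30%, so adjusting for a useless covariate costs almost nothing. Simulation with normal data (20,000 trials per value) gave 85.2%, 90.9% and 97.8% at rho 0.3, 0.5 and 0.7.

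**Step 3. Chance imbalance.** The arm difference in mean T00 has SE = 10 × √(2/35) = 2.39 lines, with a 95% range of ±1.96 × 2.39 = ±4.7. With equal SDs, an imbalance shifts the unadjusted estimate by rho times its size.
- At one SE and rho 0.5: 0.5 × 2.39 = 1.2 lines, or 17% of the 7-line target.
- At the 95% limit: 0.5, 1.4, 2.3 and 3.3 lines for rho 0.1, 0.3, 0.5 and 0.7, or 7%, 20%, 33% and 47% of the target.

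**Step 4. Is relative change a substitute?** This was simulated with a skewed baseline above 15 (16 plus a gamma variable with shape 2 and scale 7), outcome SD 10, effect −7 and counts floored at zero.
- At rho 0.1, 0.2 and 0.3, relative change has 71%, 74% and 78% power, below the roughly 82% of the raw end count.
- At rho 0.5, 0.6 and 0.7 it has 89%, 93% and 97%, against 91%, 94% and 98% for ANCOVA.

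These figures depend on the assumed distributions. The simulation does not model stopping once the count reaches 15 or fewer.

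**The case against.** Four stronger readings are tempting, and the documents support none of them.

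- *The plan excludes T00 from its primary model.* The covariate list serves a logistic, event-based model, not a comparison of counts, and its wording is open-ended. T00 is not prespecified, but it is not ruled out. Section 10.4.2 also tabulates and tests baseline characteristics for imbalance, although that does not adjust for it.
- *The unadjusted result would be biased, or the 82% is wrong.* Randomization keeps the unadjusted test valid, and the 82% reproduces.
- *Relative change takes no account of the starting count.* It does, and it comes within about 1 to 3 points of ANCOVA at rho 0.5 to 0.7. It does poorly at low rho, and the plan gives it no method.
- *A large gain is assured.* Rho is unknown. Entry is cut at more than 15 lines, and section 4.1 continues the protocol until 15 or fewer lines or 6 hours. Treating towards a common target could pull final counts together whatever the start. At rho 0.1 to 0.2 the gain is only 0.4 to 1.5 points.

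The plan also calls itself a small exploratory pilot. That limits the consequence, but the plan still claims power and tests at 0.05, and precision is scarce at 70 patients. What stands after these objections is the missing model and a nearly free improvement of uncertain size.

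**Conclusion.** The point holds as one of precision and prespecification. Section 10.4.3 gives no model for the arm difference in the continuous primary endpoint, and no stated model for that difference uses T00. Prespecified adjustment would raise power from 82.3% to between 82.7% and 98.1% for rho between 0.1 and 0.7, and would largely remove the effect of chance T00 imbalance on the estimate. The omission is certain; the size of the gain is not. It rests on an assumed rho and, for the imbalance figures, on an assumed T00 SD of 10. The change is worth making before analysis, because the loss is negligible even if rho is near zero. It does not invalidate the design.

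**What to change.** In 10.4.3, state the following:

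> The arm difference in total B-lines at the end of ED management will be estimated by linear regression (ANCOVA) on treatment, with the T00 total B-line count always included and not subject to covariate screening. T00 and the outcome will come from the same reading source and the same scale. Intervals will use robust standard errors or the bootstrap. Relative change will be reported as supportive.

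Adding T00 to the logistic list alone would not repair the comparison of counts. Keep the 82% in 10.5 and label it as the unadjusted figure.

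Two sets of passages must be reconciled first, so that both counts are on one scale:
- **Per-sector maximum.** The counting instructions in 17.1 use 20, while the core-lab text in 17.3 uses 10. Over eight sectors the ceiling is 8 × 20 = 160 or 8 × 10 = 80.
- **Extent of central reading.** Section 4.1 has all images overread, while the training list in 17.3 has the core lab review 20% of clips. The latter may mean training clips only, and the text should say so.

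The cost is one degree of freedom and some SAP wording. No extra patients or scans are needed, since T00 is already required for entry. Central reading of both scans adds work only if it was not already intended for all images.
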